## 2.8 Key points of the background

- TAVI is a valid alternative to aortic valve replacement when indicated by Heart Team
- Current guidelines suggest performing TAVI in centers with on-site cardiac surgery
- TAVI is a safe and effective therapy when the procedure is performed by experienced operators
- The majority of complications during TAVI are access-site related complications, bleedings and the need of pacemaker. The management of these complications do not require on-site cardiac surgery
- Emergent cardiac surgery during TAVI procedure is rare (<1%)
- Despite emergent cardiac surgery, 30-day mortality is still high (more than 50%)
- The concentration of TAVI patients in few centers with on-site cardiac surgery is associated with a significant increase in the waiting time for the procedure
- The median waiting time for TAVI in Italy ranges from 2 to 6 months, with wide variability between centers and regions.
- Longer waiting time for TAVI are associated with mortality and hospital readmission for heart failure
- In inoperable or high surgical risk patients, reducing the waiting time for TAVI could have a potential positive impact superior to the potential harm of the lack of on-site cardiac surgery
- The best strategy to minimize complications during the TAVI procedure is the optimization of the indication of the Heart Team and the careful planning of the procedure by experienced operators

### 3 HYPOTHESIS

Based on this background, we hypothesize that in patients with severe symptomatic aortic stenosis (inoperable or at high surgical risk) TAVI procedure can be performed by experienced operators in centers without on-site cardiac surgery (CS) with a similar 1-year outcome compared to centers with on-site cardiac surgery. Indeed:

- Bleeding, access site-related complications, and pacemaker implantation are the most common complications of TAVI and their treatment does not require on-site cardiac surgery
- Complications needing emergent cardiac surgery are very rare (<1%) and, despite the surgical intervention, the mortality in this population remains very high (more than 50% at 30 days, near 80% at 1 year)
- A median waiting time for TAVI around 3 months before TAVI is associated with a risk of mortality and hospitalization for heart failure around 4% and 15%, respectively. There is a relatively constant increase in the probability of death or of hospitalization with increasing waiting times, with no threshold below which events rates flat.
- To allow the treatment of inoperable or high surgical risk patients in centers without on-site cardiac surgery, can significantly reduce the waiting time for TAVI (also in the center with on-site CS) and then the fatal adverse events that occur between the indication for TAVI and the TAVI itself.

Therefore, we assume that an indication shared by an experienced Heart Team and a procedure meticulously planned and performed by experienced operators are the most effective strategies to minimize periprocedural complications, independently of the presence or absence of on-site CS. This hypothesis is indirectly confirmed by preliminary analyses from centers performing TAVI without on-site CS. Therefore, the aim of the TRACS trial is to investigate if a TAVI pathway based on experienced operators who perform the procedure in the center without on-site cardiac surgery is non inferior compared to the one with the same team who perform the procedure in the center with on-site cardiac surgery in terms of outcomes..

## 4 STUDY ENDPOINTS

### 4.1 Primary efficacy endpoint

- 1-year cumulative occurrence of all-cause death, stroke and hospital readmission for CV cause

To test if a TAVI pathway based on experienced operators who perform the procedure in the center without on-site cardiac surgery is non inferior compared to the one with the same team who perform the procedure in the center with on-site cardiac surgery.

### 4.2 Secondary efficacy endpoints

- All-cause death
- Cardiovascular death
- Myocardial infarction
- Hospital admission for cardiovascular cause
- Hospital admission for heart failure
- Cerebrovascular accident
- Ischemic stroke
- Hospital admission for pneumonia ( $\pm$  respiratory failure)
- Need for balloon aortic valvuloplasty for emergent condition
- Quality of life measured with the Eq-5D and KCCQ-12 scales
- Time spent on the waiting list before TAVI

### 4.3 Primary safety endpoint

- Death due to periprocedural complications actionable by emergent cardiac surgery

To test whether mortality due to periprocedural complications actionable by emergent cardiac surgery differs between the TAVI procedures performed in the center without on-site cardiac surgery and the TAVI procedures performed by the same team in the center with on-site cardiac surgery.

### 4.4 Other safety endpoints

- Cardiac tamponade
- Bleeding
- Kidney failure (requirement for renal replacement therapy)
- Severe aortic regurgitation (aortic regurgitation according to current guidelines)
- Multiorgan failure (failure of at least two organ systems)

- Vascular access site and access related complications
- Conduction disturbances and arrhythmias
- Endocarditis
- Valve thrombosis
- Valve malpositioning
- Valve embolization
- Ectopic valve deployment
- TAV-in-TAV deployment

## 5 STUDY DESIGN, SCREENING, INCLUSION AND RANDOMIZATION

### 5.1 Study design

The TRACS is an all-comer, prospective, randomized, multicenter, open-label trial with blinded adjudicated evaluation of outcomes (PROBE).

[figure not shown]
Participating centers of the TRACS trial are “**centers without on-site cardiac surgery**”. A detailed list of the criteria required for being considered participating center is reported in the section number 9 (study definition). The final decision on inclusion or not of a participating center is on charge of the Data Safety Monitoring Board (DSMB).

Each participating center must identify:

- The “**study Heart Team**”
- The “**study TAVI operators**”

A detailed description of the study Heart Team composition and role and of the criteria required for being considered study TAVI operator is reported in the section number 9 (study definition). The final decision on the accreditation of the TAVI operator in the study is in charge of the Data Safety Monitoring Board.

The figure below summarizes the main characteristics of the study flow.

[figure not shown]

## 5.2 Identification of the participating centers

The Steering Committee will proceed by inviting potential participating centers. Centers interested in participation must report data regarding organization, activity, and outcome of Heart Team discussion, TAVI selection workflow, collaboration with the referring center with on-site cardiac surgery, waiting time for TAVI, TAVI procedure, TAVI operator experience. The source documents and data will be verified by the DSMB. The DSMB is in charge to accept or not the center for the participation in the study.

## 5.3 Screening of the patients

The indication to TAVI, the screening of the patients and the eligibility for the study will be performed and shared by the “**Study Heart Team**” of the participating center (see Section 9 for detailed description). After the collection of all the required exams (i.e., transthoracic echocardiography, clinical history, laboratory exams, coronary artery angiography, computed tomography for the assessment of aortic box and vascular accesses), the Study Heart Team will agree with the indication to TAVI. After the indication to TAVI, the Study Heart Team will screen the eligibility for the study. **Eligibility for the study must be agreed and confirmed by all the components of the Study Heart Team.** All the components of the Study Heart Team of the participating center must sign a dedicated eligibility sheet. After Study Heart Team confirmation, the study will be discussed with the patient and relatives (see section 9 for the detailed description).

## 5.4 Study discussion and informed consent

The study investigator will discuss with the patient and the relatives the study design and procedures. The study investigator will clarify the strengths and limitations of the study. The potential risks related to study

participation will be detailed, as well as the potential alternatives. Only after adequate discussion, the patient will sign the informed consent. Patients can be randomized only after the signature of the informed consent.

## 5.5 Randomization

Randomization will be performed after the signature of the informed consent. Randomization will be performed centrally using an internet-based system. The patient identification number (Patient ID) and the treatment allocation will be assigned by the central randomization system. Treatment allocation will be assigned according to a computer-generated randomization list stratified by center. Randomization will also be stratified by sex, surgical risk (inoperable vs. other), age (<85 vs. ≥85 years) and valve (self-expandable vs. balloon-expandable). Patients will be randomized to the following:

- EXPERIMENTAL ARM: TAVI WITHOUT ON-SITE SURGERY
- CONTROL ARM: TAVI WITH ON-SITE CARDIAC SURGERY

All patients who are randomized are irrevocably in the study, whether or not they are subsequently found to be eligible, or actually receiving the allocated treatment. Therefore, all patients must be followed until the prespecified study end date.

## 5.6 Measures to minimize/avoid bias

The trial is open-label. Despite the obvious benefits of a double-blind design, the hospital where the TAVI intervention is performed cannot be concealed to the operator or the patient. An independent Clinical Event Committee (CEC) will adjudicate all endpoints. The CEC members and the CEC management team will be completely blinded to the randomization, as well as patient identifying information. The CEC will adjudicate the events based on predetermined definitions outlined below (VARC-3 consensus document). Other measures to avoid or minimize bias introduced by the open-label design will include intent-to-treat principles of analysis and use of objective measures for endpoint classification. An additional bias can be that some patients may receive a valve type different from that declared at the time of the randomization. This bias may occur as a consequence of factors and/or variables that emerged after randomization and immediately before the procedure or during the procedure itself. Being crucial that the distribution of self-expandable or balloon-expandable valves would be similar between study groups (despite current literature not reporting significant difference in the outcomes in the comparison of self-expandable vs. balloon-expandable), these data will be strictly monitored and eventual correction to the randomization list will be applied to avoid any unbalance. The Academic Research Organization staff will monitor the type and brand of the valve. This activity will be independent and with the aim of guaranteeing the equal distribution of valves between study arms. Any potential bias and difference will be reported by the ARO team to DSMB, which will be in charge to decide and to suggest possible corrective maneuvers.

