### 7.3 General information regarding TAVI procedure

TAVI procedure will be performed in accordance with current guidelines and institutional standards. TAVI procedure will be performed by the study TAVI operators. The decision regarding site access management, valve type and size will be left to study TAVI operators. The monitoring after the TAVI procedure and the subsequent mobilization and management of the patient will be in accordance with current guidelines and institutional standards.

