## 7.8 Role of the Data Safety Monitoring Board (DSMB)

The DSMB is responsible for the following items:

- Approval of the participating centers
- Approval of the study TAVI operators
- Analysis of the rate of adverse events in the study arms
- Monitoring of study conduction and of the distribution of valve type and valve brand between study arms

The DSMB is responsible for immediately stopping the trial if the rate of adverse events would be higher than expected. DSMB will strictly monitor the rate of periprocedural complications that require emergent cardiac surgery in the experimental arm and the rate of adverse events while on the TAVI waiting list in the control arm.

Based on previous studies, we assume that the rate of periprocedural complications requiring emergent cardiac surgery should not exceed 2% (minimum number of patients for the analysis n=75), whereas the rate of adverse events during the waiting time for TAVI in the control arm should not exceed 15% (minimum number of patients for the analysis n=100). Anyway, the DSMB:

- will be immediately informed after each periprocedural complication requiring emergent cardiac surgery
- will generate a report each 4 months illustrating the trend of adverse events (in line with or not with the expectations)
- will communicate each 4 months to the Steering Committee if the study can continue or not.

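### Section 5.6 permits correcting the randomization list to equalise the valve received after randomization, with no algorithm, trigger or firewall stated

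*Protocol*

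**What the plan says.** Section 5.5 describes central, web-based randomization stratified by center, sex, surgical risk, age and valve type (self-expandable or balloon-expandable). The Synopsis sets the ratio at 2:1, experimental to control.

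Section 5.6 then turns to a different variable, the valve implanted. It warns that "some patients may receive a valve type different from that declared at the time of the randomization", because of "factors and/or variables that emerged after randomization and immediately before the procedure or during the procedure itself". It treats a similar valve distribution between arms as crucial and states that "these data will be strictly monitored and eventual correction to the randomization list will be applied to avoid any unbalance".

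Section 7.3 gives the choice to the operators: "The decision regarding site access management, valve type and size will be left to study TAVI operators". They are not masked, since section 5.6 accepts that "the hospital where the TAVI intervention is performed cannot be concealed to the operator or the patient".

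Staff of the Academic Research Organization (ARO) monitor valve type and brand, an activity that section 5.6 calls independent. They report differences to the "DSMB, which will be in charge to decide and to suggest possible corrective maneuvers". Among the duties of that same board in section 7.8 is "Analysis of the rate of adverse events in the study arms".

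No section says how large an imbalance triggers a correction, how the list would be changed, when, or who would be kept from outcome data while deciding. No section withdraws or limits the rule.

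**The concern.** A randomization list protects the comparison because later assignments do not depend on what happened to earlier patients. Here they could. The valve received is settled after allocation by people who know the allocation, so a between-arm difference in it may be a consequence of the arm. Altering the list does not undo that difference. It offsets it by sending a different mix of later patients to each arm.

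The pre-randomization need is already addressed by stratifying on declared valve. Section 5.6 itself says that current literature shows no significant outcome difference between valve types. If that is right, the correction gains little. If it is wrong, the correction can bring in confounding by declared valve, and by whatever drives that choice.

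What is at stake is the basis of the intention-to-treat comparison in an open-label non-inferiority trial, and a procedural gap: the body that decides on corrective action also holds event rates by arm.

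**Working it through.** The protocol gives no figure for this rule and no switching rates, so there is nothing of its own to reproduce. The calculations below are illustrations under stated assumptions.

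**1. Full equalisation through the list**

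From the protocol: 2:1 ratio, so weights 2/3 (experimental) and 1/3 (control). Assumed: half of all patients are declared balloon-expandable; a fraction s of these in control receive the other type; none do so in the experimental arm; the list is adjusted until received shares are equal over the whole trial.

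Let x_c and x_e be the declared balloon-expandable shares in control and experimental.

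- Equal received shares: x_e = (1 − s) x_c
- Overall share fixed: (2/3) x_e + (1/3) x_c = 0.5
- Hence x_c = 0.5 / (1 − 2s/3)

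| s in control (0% in experimental) | Received gap, list fixed | x_c | x_e | Declared gap created |
|---|---|---|---|---|
| 10% | 5 points | 53.6% | 48.2% | 5.4 points |
| 20% | 10 points | 57.7% | 46.2% | 11.5 points |
| 30% | 15 points | 62.5% | 43.8% | 18.8 points |

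At s = 20%, the experimental share is (2/3)(0.4615)/0.5 = 61.5% among patients declared balloon-expandable and (2/3)(0.5385)/0.5 = 71.8% among the others, in place of 66.7% in both.

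If both arms switch at the same rate, (1 − s) cancels, x_e = x_c, and no gap arises.

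**2. Gradual correction**

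Simulation of 300 trials of 566 patients, half declared self-expandable (the valve labels are interchangeable for this purpose). After the first 100 patients, allocation probabilities in the two declared-valve groups are reset every 20 patients, in opposite directions, by the current gap in valve received.

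- Switching 20% experimental, 5% control: the experimental share becomes 69.4% in the declared self-expandable group and 64.3% in the other. The received gap falls from 7.5 to 2.4 points. The declared gap is 0.694/(0.694 + 0.643) − 0.306/(0.306 + 0.357) = 51.9% − 46.2%, about 6 points.
- Switching 0% in both arms, or 10% in both: the shares stay at about 66.7%.

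**3. Scale against chance**

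Under simple allocation of 373 and 187 patients with a 50% share, the SD of the between-arm difference is √(0.25/373 + 0.25/187) = 4.5 points. A 5.4-point gap is 1.2 SD; 11.5 points is 2.6 SD.

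**The case against.** Several points on the other side have force.

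- **Conditional and unspecified.** In section 5.6 the word eventual most naturally means if needed, and corrective maneuvers need not mean changing allocation. A reader might infer that the plan will depart from 2:1. The text supports only that it allows this.
- **Differential switching may be small.** The same operators treat both arms (Synopsis), working in the same way in each (section 8.2). That argues against a 20% versus 0% contrast, so 11.5 points is an illustration and not a forecast.
- **Stratification may not balance declared valve closely.** If fully crossed, about 20 centers × 2⁴ = 320 strata share 566 patients, fewer than two each. A reader might infer that declared valve is exactly balanced by design. That holds only in expectation. Chance imbalance is nevertheless unbiased, whereas drift driven by arm-specific switching is systematic.
- **The effect on the primary result could be modest.** With an assumed 5-point difference in risk between declared-valve groups, an 11.5-point gap gives 0.115 × 5 = 0.6 points of bias; with 10 points, 1.15. The margin is 10 points.
- **Randomization would not be lost outright.** If only the probabilities changed, allocation would remain random within declared valve and period, both of which could be adjusted for. Intention-to-treat is retained. This remedy requires the changes to be recorded and used in the analysis.
- **No use of outcome data is stated.** A reader might infer that event rates will steer the list. The protocol names valve distribution as the trigger, and a DSMB that sees events by arm is normal. What stands is that no firewall separates the two roles.
- **Accreditation is separate.** A reader might also infer that approval of centers and operators should leave the DSMB. That does not follow from the list-correction sentence.

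These points limit the size of the problem. None supplies a reason to keep the rule.

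**Conclusion.** The concern holds in a limited form. Section 5.6 permits a conditional change to the randomization list, triggered by a post-randomization choice of unmasked operators. Corrective action rests with a board that sees adverse events by arm, and there is no algorithm, trigger or firewall. Such a change cannot restore baseline balance, because what it equalises is not a baseline variable.

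Harm arises only if switching differs by arm and the list is actually adjusted. In that case allocation departs from 2:1 by declared valve and over calendar time. The size depends wholly on assumed switching: about 5 points in declared valve at 10% versus 0%, 11.5 at 20% versus 0%, both with full equalisation; about 6 at 20% versus 5% with gradual correction; no systematic drift when switching is equal. The route from unblinded data to allocation is open in the plan, but its use is not stated. Once applied, a changed list cannot be undone and could only be adjusted for, so the wording should be settled beforehand.

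**What to change.** - In section 5.6, delete the statement that the list may be corrected. State in 5.5 or 5.6 that the list and the 2:1 ratio stay fixed and concealed throughout.
- In sections 5.6 and 7.8, limit the DSMB's corrective maneuvers on valve distribution to actions that do not alter allocation.
- Keep the ARO's monitoring of valve type and brand, and report valve received by arm alongside valve declared.
- Account for the declared-valve stratum in the analysis, with details left to the statistical analysis plan.

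The cost is wording in sections 5.5, 5.6 and 7.8; the sample size does not change. The downside is that some imbalance in valve received must be tolerated and reported.

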## 6 STUDY POPULATION

### 6.1 Inclusion criteria

3. Severe aortic stenosis
4. Indication to TAVI confirmed by the Study Heart Team

AND one of the following:

4. Inoperable due to prohibitive operative risk \*
5. High surgical risk as defined as STS score >8% \*
6. The presence of at least one clinical factor compromising the benefit/risk ratio in the case of emergent cardiac surgery \*:

- Porcelain aorta or severely atherosclerotic aorta
- Frailty/Reduced physical performance
- Cognitive impairment, dementia, or Parkinson's disease
- Severe liver disease/cirrhosis
- Hostile chest
- Internal mammalian artery or other critical conduit(s) crossing midline and/or adhering to the posterior table of the sternum
- Severe pulmonary hypertension and/or severe right ventricular dysfunction
- Age ≥85 years
- Severe Chronic Obstructive Pulmonary Disease (COPD)

**\*: It is mandatory for the inclusion in the study that the Study Heart Team confirm by unanimous judgment the eligibility of each single patient. As described below, it is in charge of the Study Heart Team to weight the feasibility and eventual efficacy of emergent cardiac surgery and based on this assessment to proceed with the eligibility. If the Study Heart estimates the emergent cardiac surgery feasible and potentially effective, the patient cannot be considered eligible.**

### 6.2 Exclusion criteria

1. Unsuitable for transfemoral TAVI
2. Emergent TAVI
3. Noncardiovascular comorbidity reducing life expectancy to <1 year
4. Any factor precluding 1-year follow-up
5. Refusal of informed consent

## 7 STUDY PROCEDURES

### 7.1 Experimental arm: TAVI without on-site surgery

After randomization, the study TAVI operators of the participating center will schedule the patient for TAVI in their hospital without on-site surgery.

### 7.2 Experimental arm: TAVI with on-site surgery

After randomization, the patient will immediately be placed on the waiting list of the referring center with on-site surgery. The study TAVI operators of the participating center will perform the TAVI procedure in the hospital with on-site surgery according to the waiting list schedule of the latter.

